  - Based on patient feedback, to reduce participant burden because SARS-CoV-2 symptoms may be present, we will offer the opportunity for patients to self-screen online to avoid burden and barriers to participating
    - This will be performed via a web-based form. Eligibility criteria and medical history will be by self-report entries into the secure web-based form.
    - After self-screening online, patients may elect to self-consent online, or have a consent discussion with an RC (section 5.4).
  - For patients who do not want to screen or consent via web-based form, screening and consent may be done over the phone with RC with eligibility criteria and history entered into the web-based form by the RC.
  - Patients will be asked to submit proof of their positive SARS-CoV-2 result via secure means, but the receipt of the result may occur after enrollment.
    - 5.3.1 GFR

GFR will be collected on persons > age 75 years or persons of any age who select or respond that they have chronic kidney disease, heart failure, or liver disease if a GFR is not available within 2 weeks in the EHR. It may be collected from patients by either self-collection kits sent to patients' homes with return arranged by the study team; or by local in-person collection.

Participants will receive the study drug at the same time as the GFR testing kit in the mail (or GFR drawn in person), as well as a return envelope for the study drug. They will start the study drug before their GFR result is returned. If the GFR result returns and is < 45ml/min, they will be asked to stop taking the study drug and return the remainder of the study drug. This will count as a screen failure.

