## 6.0 Study Population

6.1 Study Population:

Adults age 30-85 years with no prior history of SARS-CoV-2 infection and with BMI in overweight or obesity category. We will not exclude patients who have diabetes, but we will exclude patients on insulin or a sulfonylurea. Symptoms are not a requirement to enroll in the because of their subjective nature and because of wanting to start patients on study drug early in the disease course.

6.2 Inclusion and Exclusion Criteria:

Inclusion criteria	Exclusion criteria
- Positive laboratory test for active SARS-CoV-2	- Hospitalized, for COVID-19 or other reasons.
viral infection based on local laboratory standard	- Symptom onset greater than 7 days before
(i.e. +PCR) within 3 days of randomization.	randomization (symptoms not required for inclusion).
- no known history of confirmed SARS-CoV-2	- immune compromised state (solid organ transplant,
infection	bone marrow transplant, AIDS, on chronic high dose
- Age $\geq$ 30 years and $<$ 85 years	steroids)
- BMI $\geq 25$ kg/m  by self-report height/weight or	- Hepatic impairment (Child-Pugh B and C) or
$>= 23 \text{kg/m}^2$ in patients who self-identify in	that in the opinion of the investigator, would affect safety
Asian or Latinx background. 	- Inability to obtain informed consent
- Has an address and electronic device for	- Enrollment in another blinded RCT for COVID-19
communication	- Already received an effective (FDA approved/EUA*)
- GFR>45ml/min within 2 weeks for patients	therapy for COVID-19 (currently monoclonal antibody
>75 years old, or with history of heart, kidney, or	treatment)
liver failure.	- Alcohol use disorder

- Other unstable medical condition or combination of home medications that in the view of the PI make it unsafe for the individual to participate

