
 
History of severe kidney disease i.e.:
 
Stage 4 or 5 CKD, or Estimated Glomerular Filtration Rate (eGFR) of < 45ml/min/1.73 m^2
 
Other kidney disease that in the opinion of the investigator would affect clearance
 
Unstable heart failure (Stage 3 or 4 heart failure)
 
Current use of metformin, fluvoxamine, or ivermectin
 
Bipolar disease: individuals who report they have bipolar disorder or are taking medication for bipolar disorder (lithium, valproate, high-dose antipsychotic), unless the investigator concludes that the risk for mania is unlikely (i.e. it is doubtful that the patient actually has bipolar disorder).
 
allergic reaction to metformin in the past
 
allergic reaction to ivermectin in the past
 
allergic reaction to ivermectin in the past
 
current loa loa or onchocerciasis infection
 
typhoid, BCG, or cholera vaccination within the 14- days or 3 days after
 

 
Medication Exclusions:
 
cimetidine, hydroxychloroquine, insulin, sulfonylurea, dolutegravir, patiromer, ranolazine, tafenoquine.
 
rasagiline, selegiline, or monoamine oxidase inhibitors, linezolid, methadone
 
Duloxetine, methylene blue
 
Tizanidine, ramelteon, sodium picosulfate
 
Alosetron, agomelatine, bromopride, dapoxetine, tamsimelteon, thioridazine, urokinase, pimozide
 

The following medications may not need to be excluded when dose for that individual is considered alongside the low dose of fluvoxamine being used and other medications being used. The PI or site PI may review and decide if the patient should be excluded from the fluvoxamine arms:
1. Taking SSRIs, SNRIs, or tricyclic antidepressants, unless these are at a low dose such that a study investigator concludes that a clinically significant interaction with fluvoxamine (ie either serotonin syndrome or TCA overdose) is unlikely (examples: participant takes escitalopram but only at 10mg daily; that dose plus 100mg fluvoxamine would be insufficient to cause serotonin syndrome; or, participant takes amitriptyline but only at 25mg

	nightly; even if fluvoxamine inhibits its metabolism, it would be an insufficient dose to cause QTc prolongation or problematic side effects). Risk Class C, monitor therapy .

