- We are requiring a baseline GFR in persons > age 75, or with history of heart, liver, or renal failure, within 2 weeks before enrolling to ensure those high risk patients have a GFR > 45.

Fluvoxamine:

- We are using a low dose of fluvoxamine with only 1 dose on the first day to mitigate side effects from BID dosing on the first day.
- Ivermectin:
- While the range of acceptable and safe per kilo doses of ivermectin is large, we are using weight-based dosing.

All arms:

- We will use careful screening of exclusion criteria so that participants are excluded from arms that may include a contraindication or medication interaction.
- We are recommending that study drug be taken at the end of a small meal, and that patients abstain from alcohol use during the study period.
- We are creating an upper age limit in order to reduce the likelihood of a patient experiencing reduced GFR during the study period.
- Patients will be advised to let their providers know that they are in a research study that involves metformin, ivermectin, or fluvoxamine, and thus that they should discontinue the study medication at the time of hospitalization or before a CT scan with contrast.
- Every effort will be made to enter a Research Note into the electronic health record stating that the patient is in a double-blinded randomized trial of metformin, fluvoxamine, ivermectin, and placebo with the study number and contact information for participants who are enrolled from participating health systems.
- 9.2 Reproduction Risks:

While fluvoxamine and ivermectin may be used in pregnancy and have no known teratogenic effects, they have not been assessed in prospective randomized trials in pregnancy as often as metformin has. Thus, we will close the randomization arms that include ivermectin or fluvoxamine to pregnant women. We will have a separate group of blinded study packs for pregnant and lactating women, so that study staff will know that pregnant and breastfeeding participants are getting only either metformin or placebo, but will remain blinded to whether they are receiving metformin or placebo. Additionally, because pregnant and lactating women will be considered their own sub-study in this trial, and an important sub-study, we will enroll pregnant/lactating women down to age 18 years old. Thus, pregnant women may be analyzed as a separate substudy.

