## **12.0** Statistical Considerations

A detailed statistical analysis plan (SAP) will be included as an appendix and developed by the statisticians prior to analyzing unblinded data. The SAP may be amended as needed thereafter by the blinded statistician(s). All analyses will follow a modified intention to treat (mITT) approach, excluding participants who were screen failures or who did not ingest any study drug, unless specified otherwise.

12.1 Randomization:

Eligible and consenting participants who test positive will be enrolled and randomized evenly among the arms for which they are eligible, i.e. 1:1:1:1:1:1 for participants who are eligible for all 6 arms. Randomization will be stratified by study site from which their IP is dispensed. Stratum specific schedules will be preemptively generated using mass-weighted urn randomization with a total mass of  $\alpha = 6$ , which is a generalization of randomly permuted blocks that reduces predictability of future assignments. Patients eligible for one study drug and ineligible for another, who are still interested in the trial, may be randomized amongst the study drug arm for which they are eligible. Randomization schedules will be generated for each possible drug eligibility pattern, and assignments will be drawn sequential from each stratum specific sequence therein. Statistical analyses will be study drug specific and consist of all participants who were eligible for and randomized into the relevant arms. Direct comparisons of study drugs and evaluation of drug-drug interactions will be conducted amongst participants who were eligible for both drugs in the comparison/interaction.

12.2 Blinding:

Study drug will be prepared by an unblinded study pharmacy team. Study personnel and participants will be blinded to participant assignments and outcomes data for the duration of the study, excepting lab data as detailed below and situations that require the blind to be broken for safety reasons. These instances will be recorded and reported to the PI and DSMB. An unblinded analysis of the laboratory outcomes from the treatment cohort sub-study will be carried out by the unblinded statisticians and shared with the blinded investigators and potential sponsors of the trial.

12.3 Sample Size Assumptions:

The statistical design is for the comparison of metformin vs placebo, controlling for the effect of fluvoxamine and ivermectin.

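### The allergy exclusions in 6.2, as shown, name metformin once, ivermectin twice and fluvoxamine never, so the arm-level safeguard in 9.1 has no criterion for a known fluvoxamine allergy

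*Protocol*

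**What the plan says.** The protocol tests three drugs: metformin, fluvoxamine and ivermectin (4.1, 5.1). The exclusion list in 6.2 names all three when it deals with concurrent treatment: "Current use of metformin, fluvoxamine, or ivermectin". A little further down come three separate allergy entries. The first is "allergic reaction to metformin in the past". The second and third are identical: "allergic reaction to ivermectin in the past".

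Section 6.2 also has a discretionary exclusion: "Other unstable medical condition or combination of home medications that in the view of the PI make it unsafe for the individual to participate". A separate list there lets an investigator keep a person out of the fluvoxamine arms, but it deals only with other medicines and substances being taken.

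Section 9.1, under the measures for all arms, states: "We will use careful screening of exclusion criteria so that participants are excluded from arms that may include a contraindication or medication interaction". Section 12.1 (Randomization) says that participants are "randomized evenly among the arms for which they are eligible", with a separate schedule for each pattern of drug eligibility.

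On how the criteria are applied, 5.3 allows online self-screening: "Eligibility criteria and medical history will be by self-report entries into the secure web-based form". Section 5.4 allows online self-consent without a consent conversation.

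**The concern.** In a three-drug trial, three allergy lines would be expected to cover one drug each. Here one drug appears twice and one is absent, which looks like a drafting slip.

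The slip matters because the list is operative. The safeguard in 9.1 works by screening the exclusion criteria, and the randomisation in 12.1 depends on which arms those criteria leave open. If no criterion mentions fluvoxamine allergy, the arm-specific mechanism exists but nothing triggers it in this case. Because screening and consent can both be completed online, a conversation with study staff before randomisation is not guaranteed to fill the gap.

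What is at stake is the safety of a small group of participants. No power, error-rate or analysis figure in the protocol depends on the point.

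**Working it through.** There is no sample-size or power figure to reproduce. The check is a count of entries, a search for another criterion that would cover the case, and an allocation share.

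**Step 1: allergy entries in 6.2, by study drug**

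| Drug | Named under current use | Allergy entries |
|---|---|---|
| Metformin | yes | 1 |
| Ivermectin | yes | 2 (identical) |
| Fluvoxamine | yes | 0 |

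**Step 2: does anything else in the protocol cover a past fluvoxamine allergy?**

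- The discretionary exclusion in 6.2 concerns an unstable condition or a combination of home medications. A past reaction to a drug that the person no longer takes is not clearly either.
- The investigator-review list for the fluvoxamine arms in 6.2 concerns interactions with other medicines and substances.
- The commitment in 9.1 is general enough to include an allergy as a contraindication. It is carried out through the exclusion criteria, so it refers back to the list with the gap.
- The data items listed after the medication regimen in section 5 name comorbidities and home medications. Allergy history is not among them. Some of those lists are given as examples, so its collection is not ruled out, but nothing requires it.

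None of these supplies an explicit criterion.

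**Step 3: consequence under 12.1**

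Allocation is even across the arms open to a person, so

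share = (open arms containing fluvoxamine) / (open arms).

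The six arms are metformin, fluvoxamine, ivermectin, metformin + fluvoxamine, metformin + ivermectin, and placebo.

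- Eligible for all six: fluvoxamine is in 2, so 2/6 = 33%.
- Ineligible for ivermectin: metformin, fluvoxamine, metformin + fluvoxamine and placebo remain, so 2/4 = 50%.
- Pregnant or lactating: 9.2 restricts these participants to metformin or placebo, so 0/2 = 0%.

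These are allocation shares for a person with a known fluvoxamine allergy who passes every listed criterion. They say nothing about how many such people would present. The protocol gives no prevalence, so no expected count can be computed.

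**The case against.** **The repeated line may be a reading fault.** The eligibility table in 6.2 is visibly broken in the text copy. Two identical lines where three drugs are expected could mean that the sponsor duplicated a line, or that the copy printed one line over another. Nothing in the text settles this. Against a pure copying fault, fluvoxamine is read correctly elsewhere in the same list, and merely printing an ivermectin line twice would still leave fluvoxamine without an entry. The doubt stands, and it is why the source must be checked first.

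**Other barriers exist.** Section 5.4 has the full consent reviewed, including risks, with comprehension questions even in the online route. Section 4.7 has the pill packs labelled with every possible study drug and its dose. Section 5.5.2 plans a Day 1 contact. A person who knows of the allergy would therefore be told that fluvoxamine may be in the pack. This stands in part: these steps may stop some exposures. They are not eligibility rules, however. They depend on the participant raising the matter in a blinded trial, and the labelling and the Day 1 contact come after allocation.

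**The web form may already be right.** The form is not shown. A reader might infer that it repeats the omission and that staff apply the list to the letter, but the protocol supports neither inference. It shows only that self-screening is allowed and that eligibility is entered by self-report.

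**It is only a typing slip.** That is probably how it arose. It sits in a rule that decides which arms are open to a person, so it is worth correcting despite its small size.

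**Conclusion.** The point holds in a limited form. On the text as shown, 6.2 has no allergy criterion for fluvoxamine, and 9.1 and 12.1 do not supply one. Read literally, a known fluvoxamine allergy leaves the fluvoxamine arms open: 2 of 6 arms for a person eligible for all, 2 of 4 for one ineligible for ivermectin, and none for pregnant or lactating participants.

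This rests on two assumptions: that the duplicated line is in the source document, and that screening follows the list as printed.

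Two stronger readings are tempting and not supported:

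- A reader might infer that every person with this allergy would receive the drug, or would face a uniform one-in-three chance of it. The share varies with the eligibility pattern, and consent and labelling may intervene.
- A reader might infer that participants already enrolled have been exposed, or that this could be established from study records. The protocol names no data item for allergy history, so it offers no stated source for such a check.

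The number affected is probably small. The case for correction rests on the safety consequence and the trivial cost, not on an expected count.

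**What to change.** 1. Check the duplicated allergy line in 6.2 against the source document. If the duplication is only in the text copy and the source names fluvoxamine, nothing further is needed.
2. If it is real, the sponsor should reconcile the allergy list in 6.2 with the arm-level safeguard in 9.1 and the eligibility patterns in 12.1, so that the list is consistent across the three study drugs.
3. Confirm that the web self-screening form described in 5.3, and the eligibility pattern set from its answers, match the reconciled list.

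The cost is one line of the protocol and at most one question on the form.

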2.	Individuals who take alprazolam or diazepam and are unwilling to cut the medication by 20% (rationale: fluvoxamine modestly inhibits the metabolism of these drugs). Risk Class C, monitor therapy
3.	Participants taking theophylline, clozapine, or olanzapine (drugs with a narrow therapeutic index that are primarily metabolized by CYP 1A2, which is inhibited by fluvoxamine) will be reviewed with a study investigator and excluded unless the investigator concludes that the risk to the participant is low (this would be unlikely; example: participant takes clozapine only as needed and is willing to avoid it for the 14 days of the study).
4.	Patients will be advised that there is a small risk that the following substances will be affected by fluvoxamine, but that significant effects are not likely at the low dose being used:
	1. caffeine, nicotine, melatonin. Risk Class C, monitor therapy
5.	Taking warfarin-also known as Coumadin, NSAIDs, and Aspirin (rationale: increased risk of bleeding), phenytoin (rationale: fluvoxamine inhibits its metabolism), clopidogrel (rationale: fluvoxamine inhibits its metabolism from pro-drug to active drug which raises risk of cardiovascular events), and St John's wort (rationale: fluvoxamine + St John's wort are considered contraindicated because of the risk of
	serotonin syndrome) Risk C, monitor therapy.

\*Additional COVID-19 treatments to exclude will be decided by a panel of at least 3 Co-Investigators on this study. The additional treatments to exclude will be documented and submitted to the IRB but may be implemented before formal IRB approval is complete. We take this approach because of the rapidly changing treatment landscape of COVID-19.

6.3 Vulnerable Populations:

By nature of the disease and the fact COVID-19 is a rapidly evolving pandemic, with uncertain clinical course but potentially significant morbidity and mortality, all participants enrolled in this study are considered to be vulnerable. Some participants have additional characteristics that add to this vulnerability. Our criteria for inclusion and exclusion of each of these groups is summarized below, followed by our rationale and additional safeguards built into our study design. Our group has significant experience enrolling vulnerable patients in emergency care trials, and experience with a diverse population of potential participants in high stress situations.

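### Section 6.2 item 5 calls fluvoxamine plus St John's wort contraindicated, yet leaves a user's exclusion from the fluvoxamine arms to optional investigator review

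*Protocol*

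**What the plan says.** Protocol section 6.2 handles medications in two lists. The first, headed as medication exclusions, is unconditional; one of its lines reads "rasagiline, selegiline, or monoamine oxidase inhibitors, linezolid, methadone". St John's wort is not in it.

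The second list opens with "The following medications may not need to be excluded". That sentence goes on to make this depend on weighing the individual's dose against the low fluvoxamine dose and the other drugs in use. It then says: "The PI or site PI may review and decide if the patient should be excluded from the fluvoxamine arms". Five numbered items follow. Item 5 groups warfarin, NSAIDs, aspirin, phenytoin, clopidogrel and St John's wort, each with a reason or a shared reason in brackets. For the last it says that "fluvoxamine + St John's wort are considered contraindicated because of the risk of" the condition with which the item then closes: "serotonin syndrome) Risk C, monitor therapy".

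A general criterion in the same section excludes anyone with another unstable condition or a "combination of home medications that in the view of the PI make it unsafe for the individual to participate".

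**The concern.** A contraindication normally leads to exclusion. Here the protocol states the contraindication in its own words and then files the combination in the lenient list, where exclusion depends on a review that may or may not take place. At stake is the safety of a St John's wort user who is randomized to fluvoxamine under blinding and so cannot tell whether the interacting drug is being taken. Sites could also apply the eligibility rule differently to identical people.

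**Working it through.** No arithmetic bears on the conclusion. The check is whether any text in the protocol turns the stated contraindication into a rule.

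1. **Firm list, section 6.2.** Counting by line gives 8 + 5 + 2 + 3 + 8 = 26 named drugs or classes. St John's wort is not one of them, so this list does not exclude users.

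2. **Lead-in to the second list.** It does set a condition, namely that dose and other medications be considered. It names no dose above which a person is excluded, and its verb for review is permissive. Weighing dose may settle whether a dose-related interaction matters; it does not say what makes a contraindicated combination acceptable.

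3. **Items 1 to 4 compared with item 5.**
   - Item 1 (antidepressants) excludes "unless these are at a low dose such that a study investigator concludes that a clinically significant interaction with fluvoxamine" is unlikely, and gives worked dose examples.
   - Item 2 (alprazolam, diazepam) concerns people "unwilling to cut the medication by 20" per cent.
   - Item 3 (theophylline, clozapine, olanzapine) requires review and excludes by default unless the risk is judged low.
   - Item 4 (caffeine, nicotine, melatonin) only advises patients, but there the protocol itself describes the risk as small.
   - Item 5 adds no condition of its own to the lead-in. Yet one of its six entries is the only one in the whole list whose combination with fluvoxamine is called contraindicated.

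4. **General criterion, section 6.2.** It rests on the PI's view and does not name St John's wort. It is a second discretionary route and not a rule.

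5. **Section 4.2.** The low-dose argument about serotonin syndrome is applied there to people already on an SSRI. It does not mention St John's wort.

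6. **Section 9.1.** It describes screening as the means of keeping people out of arms where a contraindication or interaction may apply. That is the aim; item 5 does not secure it for this combination.

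7. **Route to an investigator.** Section 5.3 allows eligibility and history to be self-reported in a web form, and section 5.4 allows online self-consent without a consent conversation. With optional review, nothing in section 6.2 requires a St John's wort user's case to reach an investigator.

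No step yields a firm exclusion. The text therefore permits admission of a user to the fluvoxamine arms.

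**The case against.** The best defence is that item 5 sits in the exclusion column, is phrased as an exclusion, and gives the contraindication as the reason for it. On that reading a user is excluded unless the PI, with the warning in the same line, decides otherwise. The general home-medication criterion and the stated aim in section 9.1 point the same way, and section 5.5 plans contact every two to three days to look for adverse events. This reading is fair, and it means that the protocol does not direct sites to enrol such people. What it leaves standing is a waiver, without a stated criterion or mandatory review, for a combination that the protocol calls contraindicated.

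Three stronger readings are tempting and do not hold:

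- A reader might infer that use is allowed without any condition. The lead-in's consideration of dose and other drugs applies to item 5 too; the weakness is that it has no threshold.
- A reader might infer that the protocol grades this specific combination as needing monitoring only. The grade closes an item of six entries and may be meant for the other five. The accurate statement is that nothing separates St John's wort from it. The conflict with the lead-in remains even if the grade is set aside.
- A reader might try to bound the number exposed from the enrolment still to come. The documents give no frequency of use. The fluvoxamine share also varies under section 12.1: 2 of 6 arms for someone eligible for everything, but 2 of 4 for someone ineligible for ivermectin. No defensible count follows.

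**Conclusion.** The point holds as an internal inconsistency in the eligibility criteria with a safety consequence. A combination that the protocol calls contraindicated is left to discretionary handling, and no other section closes the gap. It concerns one of six entries in item 5 and only the two fluvoxamine arms. The number of people affected is unknown and may be very small, and nothing in the documents shows that a site has admitted or would admit a user. The primary endpoint, the power and the type I error rate are not affected. The conclusion rests on the protocol's own description of the combination and needs no outside pharmacology. If the sponsor holds that the low dose makes the combination acceptable, then the word contraindicated is wrong and should be replaced by the condition for use; either way the text needs to change.

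**What to change.** Remove St John's wort from item 5 and add a firm rule to section 6.2: current use makes a person ineligible for the fluvoxamine arms (fluvoxamine alone and metformin plus fluvoxamine). The monitoring grade then no longer reaches it, and the other five entries stay as they are. Users remain eligible for the other arms. Section 12.1 already generates schedules for each pattern of drug eligibility and analyses each drug among those eligible for it, so neither the randomization nor the analysis needs redesign.

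Requiring the product to be stopped is a possible alternative, and item 3 already contemplates avoiding a drug for the 14 days. It would need a stated interval before the first dose, which the protocol does not give, so the plain exclusion is simpler.

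The cost is one entry moved in section 6.2, a matching line on the screening form, and the loss of an unknown, probably small, number of participants from the fluvoxamine comparison.
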